1.0 STUDY SUMMARY

1.1 Synopsis

Full Title	Intervention Feasibility Study - Fatherhood After Prison: Healthy Children and Families
Short Title	Pathways for Parents After Incarceration Feasibility Study
Protocol Number	MRR IRB 2020-0144
ClinicalTrials.gov Identifier & Summary	
NCT04525703
 
The purpose of this study is to learn how to better support fathers and their families after incarceration. It will test an intervention that promotes healthy development for children of previously incarcerated fathers and the caregivers of their children for empirical promise through a pilot feasibility trial. About 15 families (15 fathers, 15 caregivers, and 15-20 children, totaling 45-50 participants) will be in the study.

Number of Site(s)	UW Madison
Phase	NA
Main Inclusion Criteria	
Fathers:
 
 • being able to speak and read English • having at least one child between the ages of 3 and 17-years-old • having been released from incarceration within the last 5 years (from county jail or state/federal prison) • play a parenting role in at least some way (e.g., residence, contact, phone, etc.) 
Caregivers:
 
 • able to speak and read English • at least 18-years-old
Main Exclusion Criteria	
 • have been convicted of a crime against any of his children • are prevented from having contact with their child
Objective(s)	
The aims of the pilot are to demonstrate:
 
 • a) client acceptance of the treatment (e.g., retention) • b) ability to recruit sufficient numbers of participants • c) feasibility of delivery with the clients and therapists in the designated treatment settings
Endpoints	Key outcome measures will assess father involvement, extended family relations, and child outcomes in addition to self-report criminal behavior, substance use, and recidivism for the fathers.
Study Design	Feasibility of a behavioral intervention
FDA Regulatory Overview	NA
Study Intervention	The Pathways for Parents after Incarceration program uses eight key lessons, including topics on effective listening, speaking, and problem-solving skills, lessons on emotion regulation, and issues surrounding family engagement. The program (both classroom and therapeutic peer support) will be offered virtually and weekly for 8 continuous weeks.
Total Number of Subjects	47

Study Population	Children of previously incarcerated fathers and the caregivers of their children.
Statistical Methodology	Descriptive statistics (univariate analyses) and inferential statistics to assess differences between pre and post-test variables (bivariate analyses)
Estimated Subject Duration	The duration of the study for each subject is approximately 21 weeks including follow-up survey.
Estimated Enrollment Period & Study Duration	Study enrollment and follow-up will occur over 19 months with the total expected duration of the trial to be 19 months.

1.2 Schematic of Study Design

2.0 INTRODUCTION

2.1 Purpose

The purpose of the overall study, Promoting Healthy Development among Children of Fathers with Antisocial Behavior, is to build and test a preventive family-focused intervention in a feasibility study that promotes healthy development for children of previously incarcerated fathers and their children. The study has three specific aims, two of which have already been completed. The first was to conduct secondary data analyses to explore a series of questions that explored topics including fathers' history of antisocial behavior and criminality, children's psycho-social and behavioral health outcomes, father engagement and parenting behavior, maternal parenting practices, quality of parental relationship, and extended family involvement. The second aim included conducting semi-structured interviews with fathers, mothers, and relatives to improve understanding of the barriers to father engagement and challenges that families face as fathers return to the community following incarceration.

To that end, this protocol situates itself within the third and final aim, that of specifying treatment procedures (e.g., develop manuals, select measures, specify therapist training and adherence procedures) and establishing feasibility of the intervention (e.g., recruitment, enrollment, fidelity, adherence, retention, and safety). Specifically, this protocol is in regard to the feasibility of the intervention. The purpose is to test the intervention for empirical promise through a pilot feasibility trial. The aims of the pilot are to demonstrate: a) client acceptance of the treatment (e.g., retention), b) ability to recruit sufficient numbers of participants, and c) feasibility of delivery with the clients and therapists in the designated treatment settings.

The family intervention is based in a family systems model that includes all members of the family. Multiple family groups are used because previous research has found they are efficient forms of service delivery, build social support among participants, and improve parent-child interactions. Feasibility of the pilot must include all participants anticipated in the program model to test strategies, logistics, and measures.

Drawing from the framework of dissemination and implementation science, another central purpose of the pilot is to refine the operational methods that will facilitate translation and implementation in the future should the intervention be found efficacious and effective. This pilot will answer questions that are pertinent to intervention development, as well as the success of dissemination and implementation in the future.

2.2 Name and Description of the Study Intervention

Pathways for Parents after Incarceration is a community-based program that seeks to equip fathers with the skills both for positive father engagement and reentry success. It uses a manualized curriculum that is adapted from a prison-based program, Parenting Inside Out (PIO). PIO is an evidence-based, cognitive-behavioral parent management skills training program created for incarcerated parents through a six-year collaboration of scientists, policy makers, practitioners, and instructional designers. Both the information in the program and the way that information is presented were informed by knowledge derived from research and practice. Extracted from the full 90-hour version, the Pathways for Parents after Incarceration program uses eight key lessons from one of the original versions (PIO-48) that have been identified by the research team and those with lived experience as being most beneficial to them. These include topics on effective listening, speaking, and problem-solving skills, lessons on emotion regulation, and issues surrounding family engagement. The course is led by 2 parent coaches who will be hired and formally trained to deliver PIO by the PIO parent organization, The Pathfinder Network. The classroom-based PIO sessions will be delivered over 8 weeks in two- to two-and-a-half hour sessions. These classes will be held entirely virtually using a web-based video software. All participants will utilize computers with cameras and audio in order to join the class remotely. At no time will audio or video be recorded. All classroom components, including small group break outs and activities, will be done remotely.

In addition to the classroom component that PIO provides, the program will offer a therapeutic component. These sessions will also be done virtually. Weekly, those receiving services from Pathways for Parents after Incarceration will be invited to take part in a remote peer support group-style group session led by a provider within the community, Anesis Family Therapy. This component of the program is rooted in systems therapy and uses narrative therapy, trauma focused cognitive therapy, and motivational interviewing techniques. This aspect promotes fathers' and caregivers' ability to identify their values and skills so they can effectively confront the challenges (both instrumental and relational) that they face during their reentry period and as family members working to support the fathers. These sessions will run for 45-60 minutes following the classroom portion (PIO).

The program (both classroom and therapeutic peer support) will be offered weekly in virtual, remote format on for 8 continuous weeks (the 9th week will be a class graduation/celebration). Any participant that does not have access to a computer will be loaned laptops or tablets and internet hotspots. The structure of the sessions are as follows:

5:00pm - virtual classroom opens and PIO course activities begin
7:00pm - PIO class concludes and 30 minute break begins
7:30pm - therapeutic peer support
8:30pm - wrap up

These sessions will provide gift card or cash incentives for attending and completing class material. Food will be delivered to their home in lieu of providing food in person during group meetings as was originally planned before COVID-19.

The third and final piece of the program includes the opportunity for fathers and their families to partake in family engagement activities. Prior research pointed program development to the need to support fathers in their ability to spend time with their children engaged in prosocial activities. Pathways for Parents after Incarceration will offer monthly activities to program participants and their families which will provide families the opportunity to enhance their interactions with each other and other families in a safe way. This may include kits that the research team drops off for families centered around art, literacy, or games. It may also include virtual gatherings or outings in socially distanced venues. All decisions related to activities will be guided entirely by recommendations of Madison and Dane County Public Health Department in Wisconsin. The plan is to develop all virtual activities and then only if other formats are allowed, would we do something else.

3.0 STUDY OBJECTIVES AND ENDPOINTS

The aims of the pilot feasibility trial are to demonstrate:

- a) client acceptance of the treatment (e.g., retention)
- b) ability to recruit sufficient numbers of participants
- c) feasibility of delivery with the clients and therapists in the designated treatment settings

Specified measures will be collected at various times (e.g., client experience and satisfaction at post-intervention time points; outcome measures at pre- and post-intervention time points). Key outcome measures will assess father involvement, extended family relations, and child outcomes in addition to self-report criminal behavior, substance use, and recidivism for the fathers. Waves of data collection will occur: 1) prior to beginning the program, 2) immediately following the program, and 3) 3-months after completing the program. Data collection will be done with the father, caregiver, and child. This will be done virtually either by phone with research team members reading prompts to participants or by video conferencing where team members can virtually share screens and walk through documents together, or virtually with

research team members reading prompts and writing down answers. If not possible, it would take place in a private setting (ideally outdoors) where researchers and participants can be safely socially distanced.

4.0 STUDY DESIGN

4.1 General Design

The purpose of this pilot feasibility trial is to specify treatment procedures and establish feasibility of an intervention with the goal of identifying elements required for a randomized control efficacy and effectiveness trial in the future. The focus is on intervention procedures and assessment of feasibility as outlined in the Stage 1a and Stage 1b steps of new treatment procedures. No randomization of participants occurs. The focus is on demonstrating 1) client acceptance, 2) ability to recruit, and 3) feasibility of delivery. Data are collected from participating fathers, caregivers, and children.

4.2 End of Study Definition

The end of the study is defined as the date of the final visit completed by the last remaining subject in the study. This may be either the date of the last visit or the date of the final visit completed before that subject's participation ends (e.g., withdrawal, lost to follow-up, expiration).

5.0 SUBJECT SELECTION

5.1 Inclusion & Exclusion Criteria

Inclusion Criteria - Fathers

1. being able to speak and read English
2. having at least one child between the ages of 3 and 17-years-old
3. having been released from incarceration within the last 5 years (from county jail or state/federal prison)
4. play a parenting role in at least some way (e.g., residence, contact, phone, etc.)
5. being able to speak and read English
6. having at least one child between the ages of 3 and 17-years-old

Inclusion Criteria – Caregivers

1. able to speak and read English
2. at least 18-years-old

Exclusion Criteria

1. have been convicted of a crime against any of his children
2. are prevented from having contact with their child

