Once a study team member verifies that a father is eligible for participation and he agrees, he will provide the name and contact information of the primary or secondary caregiver (depending on the status they currently hold, themselves). The caregiver will be contacted if the child is cared for primarily by the caregiver and not the father. Individuals who are caring for the focal children of participating fathers are identified as caregivers. Based on previous research, we expect most of these caregivers to be either the other biological parent or a relative of the child.

The study team will then reach out to the caregiver to confirm interest in enrolling the child in the study through phone, text message, or email. If the caregiver does not respond or does not wish to have their child enrolled, we will notify the father that he may still enroll but that we will not be able to collect data from their child. We will place initial calls or send initial emails no more than 3 times to caregivers before ceasing communication. At that time, we will assume they are not interested in having their child participate, or themselves, and notify the father.

If a father has more than one qualifying child, one child will be randomly chosen for participation. We will not require that a child be the biological child of the participating father.

While staff at JustDane, the Beacon, Nehemiah, or the Urban League may help refer potential participants to the study, as would other service providers who have recruitment flyers at their locations, they will not actively recruit. If a potential participant were to inquire about the study or express interest, the staff at the respective agency would be instructed to refer the prospective participant to the study team for information.

All participation will be voluntary for the study respondents.

In addition to posting flyers at social service institutions, businesses, community centers, clinics, libraries, and churches with their permission, the research team will work directly with staff at community organizations (e.g., Just Dane) to share flyers and information about the study with individuals served at their agencies who might be eligible and interested. At no time, however, will staff at community agencies be asked to answer questions about the study or to explain study procedures. Instead, prospective

participants will be guided to contact the study team directly at the email address or phone number on the flyer.

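### The exclusions protect only the child, so a father under a no-contact condition protecting the caregiver alone is eligible, and the recruitment steps can link him to that caregiver

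*Combined protocol and SAP*

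**What the plan says.** The two exclusions in section 5.1, repeated in the synopsis, apply to a father who is found to "have been convicted of a crime against any of his children" or who is among those who "are prevented from having contact with their child". A caregiver must speak and read English and be "at least 18-years-old"; there is no other caregiver criterion.

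Section 5.3 sets out what follows once a father is found eligible and agrees. First, "he will provide the name and contact information of the primary or secondary caregiver". Then: "The study team will then reach out to the caregiver to confirm interest in enrolling the child in the study". This contact is limited to cases where the caregiver, rather than the father, is the child's main carer. If the caregiver declines to have the child enrolled or does not answer, the father is told that he may still enrol without child data. After three unsuccessful calls or emails the rule is: "At that time, we will assume they are not interested in having their child participate, or themselves, and notify the father". As to who these people are, "we expect most of these caregivers to be either the other biological parent or a relative of the child".

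The programme is family-based. Section 2.1 states: "Multiple family groups are used because previous research has found they are efficient forms of service delivery". Section 2.2 describes peer-support sessions intended for fathers and caregivers, and monthly activities for participants and their families. Section 9.3 counts caregivers among those who complete the intervention.

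**The concern.** The sponsor saw that convictions and contact bars matter in a recently released population, and wrote two exclusions on that basis. Those exclusions protect one of the two people whom the study connects to the father. The other is usually the child's other parent or a relative, and could be the person whom an order or a supervision condition protects.

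What is at stake is caregiver safety during recruitment. The caregiver could be approached by study staff on the nomination of a man barred from contacting them, and he would then learn from the study whether they had answered or refused. The exposure comes from recruitment steps that are written down, so it is more than a missing detail. It also bears on what section 4.1 says the pilot is for: identifying the elements of a later randomized trial, into which these criteria may be carried.

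**Working it through.** The plan states no figure on this point and no calculation applies. The check is to follow one case through the written rules: a father whose order or supervision condition bars contact with the caregiver but not with the child.

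| Step | Rule (section) | Result for this father |
|---|---|---|
| Father inclusion | English; child aged 3 to 17; released within 5 years; some parenting role (5.1) | Can be met |
| Exclusion 1 | Offence against his children (5.1) | Not triggered |
| Exclusion 2 | Bar on contact with the child (5.1) | Not triggered; an order covering both child and caregiver would trigger it |
| Caregiver criteria | English; adult (5.1) | Can be met |
| Nomination | Eligible father supplies the caregiver's details (5.3) | Proceeds |
| Staff contact | Only if the caregiver is the main carer (5.3) | Proceeds if so; the condition concerns care of the child, not safety |
| Report to father | On non-response or refusal (5.3) | Proceeds |

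None of the 2 exclusions and none of the 2 caregiver criteria refers to a restriction or offence involving the caregiver.

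The remaining question is whether anything elsewhere would stop the sequence.

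- **Enrolment check (7.1).** Screening documentation must be complete and the person deemed eligible, and the principal investigator verifies the inclusion and exclusion criteria. The investigator's verification refers back to the lists above. The screening documentation is a separate requirement, and its content is not shown.
- **Screener (8.1).** There are 11 eligibility questions. Section 5.1 has 4 distinct father inclusion items (items 5 and 6 repeat items 1 and 2) and 2 exclusions, so 4 + 2 = 6 distinct criteria. The extra questions may only split those six, or may ask something further; the documents do not settle it. No listed criterion would exclude a father who disclosed a caregiver-only restriction.
- **Supervising agent (5.2).** The study does not notify a probation or parole agent unless the participant asks or requires it, so no planned step would bring such a condition to light by that route.
- **Voluntariness (5.3).** A caregiver can refuse, but only after being contacted, and the father is then told.
- **Risks (10.2, 10.3).** Five risks are listed: confidentiality breach, upset, disclosure of sensitive information, disclosure of illegal behaviour, and fatigue. None is a risk to the caregiver from the father, and no mitigation addresses one.

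No passage shown closes the route.

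**The case against.** The best defence is that the route is narrow and partly guarded. Contact is made only where the caregiver is the main carer. Orders that also cover the child are already caught. Classes and groups are virtual, licensed clinicians lead the therapeutic groups, interviews are private, the father supplies details he already holds, and calls and emails stop after three attempts. The unseen screener and phone scripts may already ask about this. All of that stands as a limit on how often the problem would arise. None of it is a stated check on caregiver safety before contact, and the privacy and virtual-format safeguards do not act on the nomination and report-back steps.

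A reader might infer more than the documents support:

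- **That a father and his caregiver attend the same session.** The family-group and peer-support descriptions suggest it, but no passage says so. The point rests on section 5.3.
- **That a probability can be attached.** The documents give no rate of such restrictions. Any assumed rate applied to 15 families would give the chance that a restricted father is present, not the chance that the study links or harms anyone.
- **That the trial could generate the recidivism it measures.** Recidivism is named as an outcome but not defined, and 5.3 describes contact by staff, not by the father. Whether that contact breaches a condition is a legal question that the documents do not address.
- **That every past conviction for an offence against the caregiver should exclude.** With no limit on time or type of offence, this could remove families from a small pilot whose programme, under 6.1, includes co-parenting. It is a trade-off, not an evident error.

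**Conclusion.** The concern holds in a limited form. Under the listed criteria, a father with a no-contact condition that protects only the caregiver is eligible. Where the caregiver is the child's main carer, the stated recruitment steps lead to study contact with that person, and to a report back to him if the caregiver refuses or does not respond. This should be corrected.

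The size is qualitative: a gap in a rule, of unknown frequency, with a potentially serious consequence for an individual caregiver. The conclusion assumes that the unseen screener and scripts contain no binding question on the matter. If they do, the remedy is to bring that question, and what follows from the answer, into 5.1 and 5.3. The point does not affect the statistical analysis in section 9.

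**What to change.** 1. **Before nomination.** Add one screener question, asked before the father names a caregiver: does any court order or supervision condition restrict his contact with that caregiver? If yes, make no study contact with the caregiver on his nomination, do not enrol the pair jointly in sessions or family activities, and allow father-only enrolment, which 5.3 already permits when a caregiver does not take part.
2. **At first caregiver contact.** Ask the caregiver privately about any such restriction or safety concern. If one is disclosed, do not enrol the pair jointly. This question comes after contact, so it supports item 1 and cannot replace it. Section 7.1 describes oral screening consent for fathers only, so a short caregiver script is needed.
3. **Notification.** Replace the report-back in 5.3 with one neutral notice to all fathers that does not reveal the caregiver's answer or decision. Non-response, refusal and disclosure should look the same to the father.
4. **Consent.** Reconcile father-only enrolment with 7.1, which bars the family when neither adult can legally consent for the child and attributes this to exclusion criteria that 5.1 does not contain. A father who lacks legal authority, and whose caregiver is not contacted, would otherwise fall under both rules.
5. **Convictions.** Leave to the sponsor and the IRB whether a past conviction for an offence against the caregiver should also exclude.

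The cost is one amendment: a screener question, a caregiver question, a revised notice, and edits to 5.3 and 7.1. A few families may enrol as father only or not at all, which reduces caregiver and child data in a pilot of about 15 families.
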